	APPENDIX C: DEFINITION OF THE TERM “TREATMENT-EMERGENT” WITH RESPECT TO AE CLASSIFICATION	28

LIST OF ABBREVIATIONS

ADI	absolute dose intensity
AE	adverse event
AML	acute myeloid leukemia
ANC	absolute neutrophil count
ATA	antitherapeutic antibodies
CBC	complete blood count
CI	confidence interval
CR	morphologic complete remission
CRc	composite complete remission (CR+CRi)
CRi	morphologic complete remission with incomplete blood count recovery
CRF	case report form
CSR	clinical study report
ECOG	Eastern Cooperative Oncology Group
EFS	event-free survival
EOT	end of treatment
HMA	hypomethylating agents
HCT-CI	hematopoietic cell transplantation-comorbidity index
IDI	intended dose intensity
IDMC	independent data monitoring committee
ITT	intent-to-treat
LFS	leukemia-free survival
MDS	myelodysplastic syndrome
MedDRA	Medical Dictionary for Regulatory Activities
mLFS	morphologic leukemia-free state
MRC	Medical Research Council
MRD	minimal residual disease
MRU	medical resource utilization
NCI CTCAE	National Cancer Institute Common Terminology Criteria for Adverse Events
OS	overall survival
PRO	Patient reported outcome
PD	pharmacodynamic
PK	pharmacokinetic
PT	preferred term
RDI	relative dose intensity
SAE	serious adverse event
SAP	statistical analysis plan
SOC	system organ class
TRM	treatment related mortality
TTCR	time to complete remission

1 INTRODUCTION

This document outlines the statistical methods to be implemented within the scope of Protocol SGN33A-005, entitled “A randomized, double-blind phase 3 study of vadastuximab talirine (SGN-CD33A) versus placebo in combination with azacitidine or decitabine in the treatment of older patients with newly diagnosed acute myeloid leukemia (AML)”. Results of the proposed analyses will become the basis of the clinical study report (CSR) for this protocol.

The purpose of this plan is to provide specific guidelines from which the analysis will proceed. All planned analyses specified in this document will be performed. Any changes to this plan, in the form of “post hoc” or “data driven” analyses will be identified as such in the final CSR. Any changes will either be reflected in amendments to this plan before the database lock or specifically documented in the CSR.

Due to safety concerns raised by the IDMC, the study was terminated early prior to the formal interim analyses planned in the protocol. Final analysis will be performed based on 240 patients randomized into the study by the time enrollment was closed. This SAP reflects the proposed analyses for the abbreviated CSR.

2 STUDY OBJECTIVES

2.1 Primary Objective

- To compare the composite complete remission (CRc) rate (morphologic complete remission [CR] and morphologic CR with incomplete hematologic recovery [CRi]) between treatment arms
- To compare overall survival (OS) between treatment arms

2.2 Secondary Objectives

- To compare the minimal residual disease-negative remission (MRD-negative CRc) rate between treatment arms
- To evaluate the duration of remission in the 2 treatment arms
- To evaluate event-free survival (EFS) in the 2 treatment arms
- To evaluate leukemia-free survival (LFS) in the 2 treatment arms
- To evaluate the safety profiles in the 2 treatment arms
- To evaluate the time to response in the 2 treatment arms
- To evaluate the 30- and 60-day mortality rates in the 2 treatment arms

2.3 Additional Objectives

- To evaluate the treatment effect of vadastuximab talirine compared to the control group on the change in patient reported outcomes (PRO) and medical resource utilization (MRU)
- To assess the incidence of antitherapeutic antibodies (ATA)
- To assess exploratory markers of clinical outcome and the pharmacodynamics (PD) of vadastuximab talirine in combination with a hypomethylating agent (HMA)

3 STUDY ENDPOINTS

3.1 Primary Endpoint

- CRc rate
- OS

3.2 Secondary Endpoints

The secondary endpoints are:

- MRD-negative CRc rate
- Duration of remission
- EFS
- LFS
- Type, incidence, severity, seriousness, and relatedness of adverse events
- Laboratory abnormalities
- Time to CR or CRi (TTCR)
- Mortality rates at Day 30 and Day 60 post the first study treatment

3.3 Additional Endpoints

- Change from baseline in PRO
- MRU based on the number of medical care encounters
- Incidence of ATA to vadastuximab talirine
- Biomarkers of pharmacodynamic effects
- Exploratory markers of clinical activity

4 STUDY DESIGN

This is a randomized, double-blind, placebo-controlled, phase 3 study designed to compare the CRc rate and OS between patients treated with HMA plus vadastuximab talirine (experimental arm) versus patients treated with HMA plus placebo (comparator arm).

Patients will be randomized in a 1:1 manner to one of the study arms, stratified by cytogenetic risk, Eastern Cooperative Oncology (ECOG) performance status, HMA, and age. Investigators may select either HMA (azacitidine or decitabine). Response will be assessed by bone marrow examination and complete blood count (CBC) conducted between Day 22 to 28 of even-numbered cycles until CR or CRi. The response assessment window may be up to Day 42 in the event of a delay in the start of the next cycle of treatment. After CR/CRi, response assessment will be performed by CBC surveillance. In addition, bone marrow examination will be conducted according to the following schedule:

- 2 cycles after initial confirmation of CR or CRi
- At the time of conversion from CRi to CR
- At the time of suspected relapse
- End of treatment (EOT), if not performed within the previous 4 weeks

Patients may continue on study treatment until progression, leukemic recurrence, or unacceptable toxicity, whichever comes first. Patients who achieve stable disease or better should receive a minimum of 4 cycles of study treatment. Progression is defined after 4 or more cycles of treatment as either a >25% absolute rise in the percent of bone marrow blast from baseline (or a proportional increase of >25% in patients with baseline bone marrow blasts >75%) or appearance of new extramedullary disease. Patients who fulfill the criteria for progression but who are still deriving clinical benefit in the opinion of the investigator may continue on study treatment.

After discontinuation of study treatment, patients who have not experienced progression or leukemic recurrence will continue to be assessed for response by CBC surveillance every 2 months through 24 months after EOT, and every 4 months thereafter, until initiation of another anticancer treatment (excluding stem cell transplant and maintenance therapy in the absence of relapse), progression, or leukemic recurrence, whichever comes first. For all patients, survival status follow up will take place every 2 months (or more frequently as needed to support analysis of the study endpoints) after EOT until death or study closure, whichever comes first.

Safety, including SAEs and early mortality, will be monitored over the course of the study by an Independent Data Monitoring Committee (IDMC).

5 ANALYSIS SETS

5.1 Intent-to-Treat Analysis Set

The intent-to-treat (ITT) analysis set will include all randomized patients. Patients will be included in the treatment group assigned at randomization regardless of the actual treatment received.

5.2 Modified Intent-to-Treat Analysis Set

The modified intent-to-treat (mITT) analysis set will include all patients from the ITT analysis set who receive any dose of blinded study treatment (vadastuximab talirine or placebo) or HMA. Patients will be included in the treatment group assigned at randomization regardless of the actual treatment received.

5.3 Safety Analysis Set

The safety analysis set will include all patients who receive any dose of blinded study treatment (vadastuximab talirine or placebo) or HMA. Treatment group will be determined using the actual treatment received, regardless of the randomization treatment assignment. Patients receiving any dose of vadastuximab talirine will be grouped into the experimental arm. Patients who do not receive vadastuximab talirine but receive any dose of HMA will be grouped into the comparator arm.

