# **6 STUDY ACTIVITIES**

## **6.1 Schedule of Events**

Adverse events and concomitant medications will be recorded from Day 1 (predose) through the safety reporting period (see Section 7.7.1.3). Day 1 is the first dose of HMA. Any study protocol-related AE should be recorded from the time of informed consent as well as any concomitant medications given for treatment of the AE. Medical resource utilization (MRU) data will be collected from Day 1 (predose) through EOT.

Separate schedule of events tables are provided for patients treated with azacitidine and those treated with decitabine (see Appendix A). Details of PK, ATA, and biomarker sampling timepoints are provided in Appendix B. Study activities are listed by visit in this section and descriptions of all study assessments are presented in Section 7.

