## APPENDIX B: PHARMACOKINETIC, ATA, AND BIOMARKER SAMPLING TIMEPOINTS

Cycle	Study Day	Timing	Window	Blood			Bone Marrow Aspirate		
				PK	ATA	Serum and Plasma Samples for Soluble Factors	Cytogenetic Risk Assessment	MRD and CD33 Expression	RNA/DNA for Molecular Profiling
Baseline/ Screening		Within 28D prior to first HMA dose				X	X	X	X
All cycles	D1	Pre-HMA dose	Within 24h		X A	X B			
	D5 or 7 C	Pre-blinded study treatment dose	Within 8h	X B		X B			
		Post-blinded study treatment dose	Within 15 min	X					
	D28		D22–28			X D		X D	X D
EOT	D30–37	Before initiation of non-protocol therapy			X	X E		X E	X E
Long-term follow-up								X F	X F

A Required in Cycle 1–4 and every fourth cycle thereafter.

B Cycles 1 and 2 only; sample obtained predose.

C Day 5 for decitabine; Day 7 for azacitidine (or Day 9 if alternative azacitidine dosing schedule used).

D Day 22–28 in even-numbered cycles until CR/CRi. Window may be up to Day 42 in the event of a delay in the start of treatment. After CR/CRi, assessed according to the following schedule: 2 cycles after initial confirmation of CR or CRi, at the time of conversion from CRi to CR, and at the time of suspected relapse.

E Only required if not conducted within 4 weeks prior to EOT.

F Only required 2 months after confirmation of CR/CRi and at the time of conversion from CRi to CR or suspected relapse.

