7.6 Safety Analyses

The safety analysis set will be used to summarize all safety endpoints.

Adverse events will be coded using the Medical Dictionary for Regulatory Activities (MedDRA, Version 19.0 or higher).

Laboratory values will be graded according to the National Cancer Institute (NCI) Common Terminology Criteria for Adverse Events (CTCAE version 4.03 or higher).

Concomitant medications will be coded using the WHO Drug Dictionary (version: June 2015 or more recent).

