7.6.1 Adverse Events

Adverse events (AEs) will be summarized by descending MedDRA preferred term (PT) unless otherwise specified. For incidence reporting, if a patient reports more than one AE that was coded to the same system organ class (SOC) or PT, the patient will be counted only once for that specific SOC or PT.

A treatment-emergent AE is defined as a newly occurring or worsening AE after the first dose of any study treatment. See Appendix C for details regarding treatment-emergent classification. Summaries of AEs will be provided by treatment group and total for the following:

- Pre-existing AEs
- All treatment-emergent AEs

- AEs related to blinded study treatment
- AEs related to azacitidine
- AEs related to decitabine
- Serious Adverse Events (SAEs)
- SAEs related to blinded study treatment
- SAEs related to azacitidine
- SAEs related to decitabine
- AEs leading to blinded study treatment dose delay
- AEs leading to azacitidine dose delay
- AEs leading to decitabine dose delay
- AEs leading to blinded study treatment dose reduction
- AEs leading to azacitidine dose reduction
- AEs leading to decitabine dose reduction
- AEs leading to overall treatment discontinuation
- AEs leading to blinded study treatment discontinuation
- AEs leading to azacitidine discontinuation
- AEs leading to decitabine discontinuation
- Grade 3 or higher treatment-emergent AEs
- Infusion-related reactions (within 24 hours of blinded study drug dose)
- Treatment-emergent AEs by SOC and PT
- Treatment-emergent AEs by SOC, PT, and maximum severity. At each SOC or PT, multiple occurrences of events within a patient are counted only once at the highest severity
- Grade 3 or higher treatment-emergent AEs by SOC and PT
- TEAEs with incidence $\geq 5\%$ by SOC and PT
- SAEs with incidence $\geq 5\%$ by SOC and PT

AEs in the categories below as defined by the Standardized MedDRA Queries (SMQs) or customized searches will be summarized by SOC, PT, and maximum severity. SAEs will be summarized by PT.

- Serious infection
- Bleeding
- Thrombocytopenia
- Neutropenia
- Anemia
- Hepatotoxicity
- Edema
- Pulmonary
- Cardiomyopathy
- Cardiac failure
- Myocardial infarction

All AEs, SAEs, grade 3 or higher treatment-emergent AEs, AEs leading to treatment discontinuation, and AEs with fatal outcome will be listed.

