7.6.5 Deaths

The number of total deaths, deaths that occurred within 30 days of last study treatment, and deaths that occurred more than 30 days after last study treatment, as well as the relationship to disease, will be summarized by treatment group and total. In addition, cause of death will be identified by descending MedDRA preferred term (unless otherwise specified) and summarized by treatment group and total. Death information will be listed by patient.

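### Experimental-arm patients who receive HMA but never a blinded dose are tabulated as comparator, so their events in the overall AE and SAE tables can move in one direction only

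*SAP*

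**What the plan says.** SAP 5.3 admits to the safety set anyone given a dose of blinded treatment or HMA, and groups by what was received. Any vadastuximab talirine makes a patient experimental. For the rest the rule is "Patients who do not receive vadastuximab talirine but receive any dose of HMA will be grouped into the comparator arm". Protocol 9.3.1.7 has the same rule.

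On timing, Protocol 6.1 states "Day 1 is the first dose of HMA". Protocol 5.2.2 and Appendix B put blinded treatment on the last HMA day: Day 5 with decitabine, Day 7 with azacitidine, or Day 9 on the alternative azacitidine schedule. SAP 7.6.1 starts the treatment-emergent clock earlier than that: "A treatment-emergent AE is defined as a newly occurring or worsening AE after the first dose of any study treatment".

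On the sets used, SAP 7.6 says "The safety analysis set will be used to summarize all safety endpoints". SAP 7.5 puts all efficacy output on the intent-to-treat (ITT) set; this covers overall survival (7.5.1.2), and 30- and 60-day mortality with cause of early mortality (7.5.2.6). SAP 5.2 defines an mITT set with the same entry condition as the safety set but a different grouping: "Patients will be included in the treatment group assigned at randomization regardless of the actual treatment received". No analysis in SAP section 7 uses it.

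**The concern.** Every patient spends the first days of cycle 1 on HMA alone, and events in those days already count as treatment-emergent. Up to the blinded dose both arms receive the same treatment under a double blind, so failure to reach that dose should not depend on the arm. Grouping as randomised keeps that balance. The SAP 5.3 rule does not: it places the HMA-only patients of both arms in the comparator column.

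The trial stopped on safety concerns raised by the monitoring committee, and the abbreviated report rests largely on safety tables. If an early death or severe toxicity is the reason the blinded dose was never given, the patient's whole AE record moves to comparator. The main AE and SAE comparisons have no as-randomised counterpart to show the effect.

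**Working it through.** **1. Where each patient goes**

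| Randomised to | Received | Safety set (5.3) | mITT (5.2) |
|---|---|---|---|
| Experimental | HMA only | Comparator | Experimental |
| Comparator | HMA only | Comparator | Comparator |
| Experimental | HMA and any vadastuximab talirine | Experimental | Experimental |
| Comparator | HMA and placebo | Comparator | Comparator |

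No HMA-only patient can enter the experimental column, so for these patients the flow is one-way. A patient with an early event who later receives any vadastuximab talirine stays experimental. Kit errors can move patients either way; they are a separate route, and SAP 7.4 lists them.

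**2. Which outputs are exposed**

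- Exposed: the all-causality AE, SAE and Grade 3 or higher treatment-emergent summaries, the HMA-related summaries, and some discontinuation summaries.
- Not exposed: tables that presuppose a blinded dose (events related to blinded treatment, infusion reactions, blinded-dose reductions).
- Unaffected, because ITT: overall survival, 30- and 60-day mortality, cause of early mortality.
- The death counts in SAP 7.6.5 fall under the safety set and so follow its grouping. Randomisation is within 1 business day before the first HMA dose (Protocol 5.2.2), so a death in the gap also appears, by randomised arm, in the 30-day mortality rate.

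**3. How many deaths might move**

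The documents give no count of HMA-only patients, so there is no plan figure to reproduce. Inputs: 240 randomised (SAP 6.10) at 1:1, taken as 120 per arm; gaps of 5 − 1 = 4, 7 − 1 = 6 and 9 − 1 = 8 days; medians of 9 and 12.9 months (SAP 6.2); 30.4375 days per month (SAP 6.4); phase 1 mortality of 4% at 60 days and 0% at 30 days in 24 patients (Protocol 3.2.2). A constant hazard is assumed.

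Expected experimental-arm deaths in the gap = 120 × (1 − exp(−h·t)), with h = ln 2 / (median × 30.4375), or h = −ln(0.96)/60 for phase 1. The mixed column puts half the patients at 4 days and half at 6. That split is an assumption, in line with the aim of balanced HMA use in Protocol 5.1. The last column is exp(−mean), from unrounded means.

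| Hazard from | 4 days | 6 days | 8 days | Mixed | Chance of none (mixed) |
|---|---|---|---|---|---|
| 9-month median | 1.21 | 1.81 | 2.40 | 1.51 | 0.22 |
| 12.9-month median | 0.84 | 1.26 | 1.68 | 1.05 | 0.35 |
| Phase 1, 60-day 4% | 0.33 | 0.49 | 0.65 | 0.41 | 0.67 |

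The phase 1 30-day rate of 0% gives zero. The 8-day column would need every patient on the Day 9 schedule. Early non-fatal stops would add to these figures.

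**4. What a move does to the percentages**

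Let k patients per arm be HMA-only with event risk r, and let all others have risk q in both arms. As randomised the arms are equal. Under SAP 5.3 the experimental rate is q and the comparator rate is [(120 − k)q + 2kr]/(120 + k), so the spurious difference (experimental minus comparator) is 2k(q − r)/(120 + k).

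- k = 1, q = 10%, r = 100%: 2 × (−0.9)/121 = −1.5 points (10.0% v 11.5%).
- k = 3, same risks: 6 × (−0.9)/123 = −4.4 points (10.0% v 14.4%).
- k = 1, q = 10%, r = 0: 2 × 0.1/121 = +0.2 points.

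The sign depends on whether r exceeds q. As a second illustration, take an assumed event at 24 v 18 of 120 (20.0% v 15.0%, 5.0 points):

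- one patient with the event moved: 23/119 v 19/121 = 19.3% v 15.7%, 3.6 points;
- two moved: 22/118 v 20/122 = 18.6% v 16.4%, 2.3 points;
- one or two moved without the event: 24/119 v 18/121, or 24/118 v 18/122, giving 5.3 or 5.6 points.

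**The case against.** The rule is an explicit as-treated choice. A patient never given vadastuximab talirine cannot have toxicity from it, and an exposure-based set properly keeps that patient out of its column. The rule stands in the protocol, which predates termination, and the SAP matches it. Regrouping now would alter a pre-specified safety grouping after the trial stopped. This stands, and is why SAP 5.3 should be left alone.

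Existing cover is also substantial. Deaths are shown by randomised arm in the ITT analyses. Disposition is listed by patient, and so are AEs and deaths (for example "AEs leading to treatment discontinuation, and AEs with fatal outcome will be listed"), and SAP 6.1 promises the clinical data as electronic data sets, so a moved patient could be traced. SAP 7.1 tabulates patients treated per randomisation assignment, and Protocol 9.3.2 summarises the size of each set. If mITT and safety-set sizes were shown by arm, their difference would give the net number moved, kit errors included. Neither output identifies HMA-only patients as such, and listings are not an arm comparison.

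The magnitude is hypothetical. A constant hazard at the 9-month median implies 1 − exp(−ln 2 × 60/273.9) = 14% mortality at 60 days, against 4% in phase 1 (itself imprecise at 24 patients). Entry also requires a life expectancy of at least 12 weeks. The lower figures may be nearer the truth. No test, boundary or decision in the SAP depends on the grouping.

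A reader might infer more: that the mortality comparison is distorted, that every safety table is tilted, or that the percentages must favour the experimental arm. The documents do not support this. Mortality and survival are ITT, tables tied to a blinded dose cannot gain moved events, and a moved patient without the event shifts the difference slightly the other way.

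**Conclusion.** The point holds in a narrow form and is minor. For HMA-only patients, SAP 5.3 lets events pass only from experimental to comparator in the all-causality AE, SAE and Grade 3 or higher summaries, and in the HMA-related and some discontinuation summaries. This follows from the wording and needs no assumption. The size does: with 120 per arm, constant hazard and mixed schedules, about 0.4 to 1.5 deaths would be expected to move, with a 22% to 67% chance that none does; the phase 1 30-day rate gives zero. Percentages move against the comparator only if HMA-only patients have a higher event risk than the others. That is plausible where early toxicity or death prevented the blinded dose, but the documents do not show it. The SAP plans neither a direct count of these patients nor an as-randomised version of the main AE and SAE tables.

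**What to change.** Keep the safety set and its as-treated tables as they are. In SAP 7.1, add the number of patients who received HMA but no blinded dose, by randomised arm. If that number is not zero, repeat the overall SAE table and the Grade 3 or higher treatment-emergent AE table on the mITT set of SAP 5.2. Record the addition in SAP section 9, labelled as made after termination. No repeat of the SAP 7.6.5 death table is needed, since the ITT analyses already show these deaths by randomised arm.

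The cost is one count and at most two descriptive tables on an existing set, with no new data. If the count is zero, the count alone settles the matter. The drawback is that the tables are a late addition and must be read as such.

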6 STATISTICAL CONSIDERATIONS

6.1 General Principles

Descriptive statistics (mean, median, standard deviation, minimum and maximum) will be used to summarize continuous variables. Frequencies and percentages will be used to summarize categorical variables. The median survival time will be estimated using the Kaplan-Meier method; the associated confidence interval (CI) will be calculated based on the complementary log-log transformation (Collett 1994).

Unless otherwise specified, all statistical tests will be performed using a two-sided alpha of 0.05. Confidence intervals will be calculated at a two-sided 95% level. Multiplicity adjustment for alpha level is discussed in Section 6.7.

Any analysis not described in this plan will be considered exploratory, and will be documented in the CSR as a post hoc analysis or a change to the planned analysis.

To comply with regulatory electronic submission guidelines, listings of all clinical data will be submitted as electronic data sets. To facilitate data review for the study report, only pertinent data listings will be created and attached to the appendix of the CSR.

All statistical tables, listings, and figures will be produced using SAS[®], version 9.3 or more recent. Other statistical software, if used, will be described in the CSR.

